For cohort two, our primary outcome is the first occurrence of either hospital admission with SARI in the HES dataset (defined as a new ICD-10 code J09-J22 in the HES dataset) or ICU admission in the ICNARC CMP dataset with SARI (defined as any admission with unique diagnostic code any one of RE129 RE131 RE82 RE50 RE86 RE94 RE75 RE133 RE132 RE121 RE1 RE128 RE16 RE130 RE117 RE42 RE41) or death. Secondary outcomes will be each of these three events considered separately (I.e. SARI related hospital admission, ICU admission, death).

Aim 2.

Our primary outcome is development of new neuropsychological disease up to 1 year following hospital discharge which we define as having received a diagnostic code as below:

- Anxiety and stress-related disorders [ICD F40-48 and corresponding Read codes]
- Mood disorders [ICD F30-39 and corresponding Read codes]
- Psychotic disorders [ICD F20-29 and corresponding Read codes]
- Dementia [ICD F00-F03, G30, G31.0 ? and corresponding Read codes]

Secondary outcomes are the diagnosis of new neuropsychological disorders (as defined above) with treatment, and where numbers are available the new diagnosis with or without treatment of each class of disorders, each considered as a separate endpoint.

Neuropsychological treatments are defined as:

- Hypnotics and anxiolytics: (hypnotics, anxiolytics, barbiturates and methyprylone, benzodiazepines)
- Antidepressant drugs (Tricyclic and related antidepressant drugs, Monoamine-oxidase inhibitors, Selective serotonin re-uptake inhibitors, Other antidepressant drugs)
- Drugs used in psychoses and related disorders (Antipsychotic drugs and depot injections, Lithium salts, Phenothiazine derivatives)

Definition of exposures

Aim 1

Neuropsychological disease will be defined as an ordinal variable with the following three categories: no relevant diagnosis or drugs; diagnosis ever recorded without recent drug treatment; diagnosis present with recent drug treatment (with at least two prescriptions for neuropsychological treatments as above within the six months preceding study entry).

Our primary exposure is active neuropsychological disease on the study entry date which we define as having received a diagnostic code as above (24th January 2020 for cohort 1 and 24th January 2015 for cohort 2).

Aim 2.

The primary exposure is a hospital or ICU admission resulting from COVID-19 infection. Comparator exposures are hospital or ICU admission resulting from SARI.

Covariates

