Sensitivity analyses

We will undertake complete case analysis in those without missing data as a sensitivity analysis of our findings.

We will also restrict analysis to only include patients with confirmed COVID-19 diagnosis using RNA testing.

For Aim 2 we will carry out a sensitivity analysis in cohort four with additional censoring of follow-up on 24th January 2020, so that outcomes are assessed prior to the pandemic period. In comparing cohort 3 and 4 we will consider the competing risk of death by undertaking a competing risk analysis.

In order to compensate for the low expected event rates relative to our sample sizes for aim 2, we will combine cohorts 3 and 4 and use all available baseline characteristics (as listed previously) to calculate a propensity score to measure the likelihood of developing a new neuropsychological condition up to 1 year after ICU admission. We will then use these scores (with inverse probability weighting) to compare the adjusted hazard of developing a new neuropsychological condition in patients admitted to critical care for COVID compared to those admitted for SARI.

The authors will have full access to anonymised data from the Case Mix Programme, QResearch and Public Health England, and Hospital Episode statistics databases. We will remove duplicate records for the same individual, and set dates and values outside a pre-defined credible range as missing. For patients admitted with SARI between 2015-2020 the full set of standard data validation processes for unit level data intended for public reporting will have been carried out by ICNARC. Some of the more recent Covid admissions will have undergone a more restricted set of validations, but these do include confirming the total number of admission with Covid to each unit, checking that duration of organ support does not exceed duration of stay, and confirming with units that that aggregated units level summaries of length of stay and organ support (among other measures) are in line with expectations. All variables used in the analysis will be initially summarised in a table of baseline characteristics to include minimum, maximum, median and quartiles.

Data linkage

Person-level data linkage will be undertaken between QResearch, Hospital Episode Statistics, the Case Mix Programme and Public Health England. Cases will be matched on pseudonymised NHS number [15].

Discussion

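### One Aim 2 sensitivity analysis builds its propensity score on the outcome instead of on COVID versus SARI, so its inverse probability weights would not adjust for confounding

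*Protocol*

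**What the plan says.** The Protocol, under Sensitivity analyses, gives the reason for the analysis as follows: "In order to compensate for the low expected event rates relative to our sample sizes for aim 2". The method has three steps.

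- Pool the cohorts: "we will combine cohorts 3 and 4 and use all available baseline characteristics (as listed previously").
- Build the score: "calculate a propensity score to measure the likelihood of developing a new neuropsychological condition up to 1 year after ICU admission".
- Apply it: the scores become inverse probability weights, and the purpose is given as: "compare the adjusted hazard of developing a new neuropsychological condition in patients admitted to critical care for COVID compared to those admitted for SARI".

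Two definitions under Variables show what role each quantity plays. The Aim 2 outcome is: "Our primary outcome is development of new neuropsychological disease up to 1 year following hospital discharge". The Aim 2 exposure is: "The primary exposure is a hospital or ICU admission resulting from COVID-19 infection", with SARI admission as comparator. Nowhere does the protocol describe a model for the probability that a patient is a COVID rather than a SARI admission.

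The main Aim 2 analysis (Statistical Methods, Aim 2) is a cause-specific Royston-Parmar model with direct covariate adjustment. It makes no use of the score.

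**The concern.** Inverse probability weighting removes measured confounding because each patient is weighted by the inverse probability of the exposure group the patient is in. After weighting, both groups resemble the same pooled population. The probability of the outcome has no such property. It is a prognostic (disease risk) score: it may serve for stratification, matching or adjustment, but its inverse does not make COVID and SARI patients comparable.

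An analyst who followed the sentence literally would report a ratio labelled as adjusted that is not adjusted. If it disagreed with the main model, a correct main result could be doubted. If it agreed, the agreement would be no evidence of robustness. This is the only propensity-score analysis in the protocol, and the section on Effect Modifiers makes covariate inclusion in the Aim 2 models depend on sample size and number of events. A weighted check would carry more weight if the main model had to be trimmed.

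**Working it through.** The protocol gives no event rate, power or effect size for this analysis, so there is no stated figure to reproduce. The check asks what the written rule estimates.

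**Inputs from the protocol (Study Size).** Cohort 3 has about 11,000 admissions. Cohort 4 has about 7,000 per year, so 5 × 7,000 = 35,000. The pooled total is 46,000 and the marginal probability of COVID is 11,000 / 46,000 = 0.239.

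**Assumptions not in the protocol.** All event rates, covariate strengths and imbalances below. The protocol also does not say how an outcome score q becomes a weight, so three rules are considered:

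- (a) 1/q for COVID and 1/(1−q) for SARI, treating q as if it were the exposure probability;
- (b) 1/q for patients with the event and 1/(1−q) for those without;
- (c) 1/q for everyone.

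**Hand check of rule (a).** Take two risk strata with q = 0.05 and q = 0.10, equally common in both cohorts, and no COVID effect. There is no confounding and the true risk ratio is 1.00.

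- COVID weights are 1/0.05 = 20 and 1/0.10 = 10. Weighted risk = (20 × 0.05 + 10 × 0.10) / 30 = 0.0667.
- SARI weights are 1/0.95 = 1.053 and 1/0.90 = 1.111. Weighted risk = (1.053 × 0.05 + 1.111 × 0.10) / 2.164 = 0.0757.
- Ratio = 0.0667 / 0.0757 = 0.88.

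The low-risk stratum forms 20/30 = 67% of the weighted COVID group but 1.053/2.164 = 49% of the weighted SARI group, although it was 50% of each before weighting. The weights create imbalance. Exposure weights would be 1/0.239 for every COVID patient and 1/0.761 for every SARI patient. Both weighted risks stay at 0.075 and the ratio is 1.00.

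**Simulation at the protocol's cohort sizes.** One covariate, one-year follow-up, yearly hazard about 12%, weighted rate ratio. The covariate lies 0.5 SD lower in COVID unless stated.

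| Weights | True HR 1.00 | True HR 1.30 |
|---|---|---|
| Exposure-based | 1.00 | 1.30 to 1.32 |
| (a), covariate HR 1.65 per SD | 0.59 to 0.60 | 0.78 |
| (a), covariate HR 1.22 per SD | 0.87 to 0.89 | 1.12 to 1.25 (top of range is without the imbalance) |
| (b) | 0.98 to 1.03 | 1.18 to 1.21 |
| (c) | about the crude ratio | about the crude ratio |

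With no imbalance, rule (a) at covariate HR 1.65 still turns a true 1.00 into 0.76. At HR 1.22 it gives 0.96 to 0.97.

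**A second set of assumptions.** Two covariates, each with log hazard ratio 0.5; one shifts the log odds of COVID by 0, +0.5 or −0.5; baseline hazard 0.05 or 0.10 per year; weighted Cox model.

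- Exposure-based weights give 0.98 to 1.01 for a true 1.00, and 1.25 to 1.31 for a true conditional 1.30.
- Rule (a) gives 0.44 to 0.74 for a true 1.00 and 0.58 to 0.94 for a true 1.30.
- Rule (b) gives about 1.00 for a true 1.00 and 1.17 to 1.23 for a true 1.30. It raises events from 6% to 12% of patients to 50% of the weighted sample.
- Rule (c) under confounding tracks the crude ratio. For a true 1.00 it gives 1.25 to 1.29 (crude 1.23 to 1.25) or 0.77 (crude 0.78). For a true 1.30 it gives 1.59 to 1.63 or about 1.02. The error can therefore go upwards when the higher-risk patients are in the COVID cohort.

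**The case against.** The strongest reply is that this is a drafting slip. The same paragraph speaks of a propensity score and inverse probability weighting, pools the two exposure cohorts and states a COVID-versus-SARI contrast, all of which belong to an ordinary exposure-propensity analysis. One clause names the wrong target, and a competent analyst might correct it silently. That is plausible and lowers the chance of harm. It does not rescue the text: the clause is explicit, nothing elsewhere contradicts it, and this is a stated rule and not a detail left for a statistical analysis plan.

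The reply on scope also stands. A reader might infer that the Aim 2 result is invalid. The documents do not support that, because the main model adjusts for the covariates directly and Aim 1 is untouched.

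A reader might also infer that the analysis would necessarily reverse or erase the COVID effect. That depends on an unstated weighting rule and on assumed covariate strength. With a weak covariate (HR 1.22 per SD) there was no reversal. Rule (b) left a true null close to 1.00. Rule (c) did no harm where there was no confounding.

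Finally, the stated rationale is low event rates relative to sample size. It is not a shortage of events per covariate, and covariate selection is addressed separately under Effect Modifiers.

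**Conclusion.** The point holds as an error in one Aim 2 sensitivity analysis. As written, the score models the outcome, and weighting by its inverse does not balance cohorts 3 and 4, so the resulting hazard ratio is not confounder-adjusted. That conclusion follows from the definitions and needs no simulation.

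The size is illustrative. With about 12% yearly hazard and one confounder of HR 1.2 to 1.65 per SD lying 0.5 SD lower in COVID, a true 1.30 becomes 0.78 to 1.21 and a true 1.00 becomes 0.59 to 1.00 across the three weighting rules. Other assumptions give other ranges, including upward bias. No outcome-based rule recovered 1.30 under confounding in either set of assumptions; exposure-based weights gave 1.25 to 1.32. The text should be corrected before the analysis is run, but the main Aim 2 conclusion does not depend on it.

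**What to change.** Change the target of the score. Define it as the probability of being in the COVID cohort rather than the SARI cohort, given baseline covariates. Weight each patient by the inverse probability of the cohort the patient is in, and check covariate balance after weighting. Details such as weight stabilisation and variance estimation can be left to the statistical analysis plan.

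If an outcome-risk score is really intended, call it a prognostic (disease risk) score, use it for stratification or adjustment, and remove the inverse probability weighting.

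Two small points can be settled in the same edit. The score's one-year horizon runs from intensive care admission, whereas Aim 2 follow-up runs from hospital discharge. The stated purpose also needs rewording, since weighting adds no events and cannot by itself make up for a low event rate.

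The cost is a sentence or two of protocol text. No additional data are needed and the main analysis does not change.

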
Figure 1: Data flow diagram for cohort 1 and cohort 2 for the antecedent study.

Figure 2: Data flow diagram for cohort 3 and cohort 4 for the antecedent study.

AIM 2 - sequelae study

COHORT 2

- age 18+ at hospital/ICU admission
- pandemic period: 24/01/20 XX
- COVID-19 ICU DISCHARGED PATIENTS (ICNARC)
- N = XX
- COVID-19 HOSP DISCHARGED PATIENTS (HES)

N = XX

ALL DEATHS (ONS) N = XX

\rightarrow QRESEARCH N = XX

- COVID-19 ICU DISCHARGED PATIENTS
- (ICNARC) n = XX COVID-19 HOSP DISCHARGED PATIENTS (HES) n = XX
- ALL DEATHS (ONS) n = XX

COHORT 3

- (to be used as compartor for COHORT 2)
- age 18+ at hospital/ICU admission
- historical cohort: 24/01/15 23/01/20
- SARI ICU DISCHARGED PATIENTS

(ICNARC)

- N = XX SARI HOSP DISCHARGED PATIENTS (HES) N = XX
- ALL DEATHS (ONS) N = XX

→ QRESEARCH N = XX

- SARI ICU DISCHARGED PATIENTS (ICNARC) n = XX
 SARI HOSP DISCHARGED PATIENTS
- (HES) n = XX
- ALL DEATHS (ONS) n = XX

Figure 3. Directed Acyclic Graph for Aim 1.

Figure 4. Directed Acyclic Graph for Aim 2.

Version history

Version	date	author	Notes
1.0	27.11.2020	PST, MP, RH, PW, CC	
1.2	12.12.2020	PST	Updated after teams meeting 11.12.20
1.3	22.03.2021	PW	
1.4	25.06.2021	PW,MP,CC,KT,DH	
1.5	23.07.2021	a/a	TR made final changes
